#### 6.6.1.1. All adverse events

Adverse events will be summarized by worst severity (according to NCI-CTCAE version 4.03) per patient, using the latest version of MedDRA preferred term (PT) as event category and MedDRA primary system organ class (SOC) body term as Body System category.

In case a patient has events with missing and non-missing grades, the maximum of the non-missing grades will be displayed. No imputation of missing grades will be performed.

The following tables will be created:

- The overall summary of AEs table will include the frequency (number and percentage) of patients with each of the following by treatment group:
  - TEAEs
  - TEAEs, Grade  $\geq 3$
  - Related TEAEs
  - Related TEAEs, Grade  $\geq 3$
  - TEAEs leading to dose reduction of avelumab
  - TEAEs leading to dose reduction of axitinib

- TEAEs leading to interruption of avelumab
- TEAEs leading to interruption of axitinib
- TEAEs leading to discontinuation of avelumab
- TEAEs leading to discontinuation of axitinib
- TEAEs leading to discontinuation of any study drug
- TEAEs leading to discontinuation of all study drugs
- Related TEAEs leading to discontinuation of avelumab
- Related TEAEs leading to discontinuation of axitinib
- Related TEAEs leading to discontinuation of any study drug
- Related TEAEs leading to discontinuation of all study drugs
- Serious TEAEs
- Related Serious TEAEs
- TEAEs leading to death
- Related TEAEs leading to death
- irAEs
- IRRs
- TEAEs by SOC and PT and worst grade
- Related TEAEs by SOC and PT and worst grade
- TEAEs related to avelumab by SOC and PT and worst grade
- TEAEs related to axitinib by SOC and PT and worst grade
- TEAEs related to any study drug by SOC and PT and worst grade
- TEAEs leading to death by SOC and PT
- Related TEAEs leading to death by SOC and PT
- TEAEs Excluding SAEs, with frequency  $\geq 5\%$  in any treatment group by SOC and PT

#### **6.6.1.2. Adverse events leading to dose reduction**

The frequency (number and percentage) of patients with each of the following will be presented for TEAEs leading to dose reduction of each study drug by treatment group:

- TEAEs leading to dose reduction of avelumab by SOC and PT
- TEAEs leading to dose reduction of axitinib by SOC and PT

The listing of all AEs leading to dose reduction will also be provided with the relevant information.

### **6.6.1.3. Adverse events leading to interruption of study treatment**

The eCRF does not allow for a clear separation between interruption of an infusion and delays of administration for a parenteral drug as both are recorded using the same term on the eCRF (“Drug interrupted”). IRRs will be excluded in the analysis of AEs leading to Drug Interruption in case they only led to an interruption of the infusion (ie, did not lead to a dose reduction or a dose delay).

As such, AEs leading to interruption will be defined as AEs identified in the AE eCRF page with an action taken with study treatment of ‘drug interrupted’ excluding

- IRRs that occurred on the day of infusion with  $\geq 90\%$  of the planned dose given (ie IRRs that did not lead to a dose reduction) and subsequent administration of study drug had no delay (as defined in Section 6.5.3.6). These IRRs will be considered as IRRs leading to interruption of infusion.
- IRRs occurring on the day after infusion and subsequent dose administration had no delay (as defined in Section 6.5.3.6).

The frequency (number and percentage) of patients with each of the following will be presented for TEAEs leading to interruption of each study drug by treatment group:

- TEAEs leading to interruption of avelumab by SOC and PT
- TEAEs leading to interruption of axitinib by SOC and PT

The listing of all AEs leading to interruption of study treatment will also be provided with the relevant information.

In addition, the frequency (number and percentage) of patients with each of the following will be presented for TEAEs leading to interruption of each study drug by treatment group:

- TEAEs leading to both interruption and dose reduction of avelumab by SOC and PT
- TEAEs leading to both interruption and dose reduction of axitinib by SOC and PT

This summary will take into account PTs with both actions as defined in Section 6.6.1, even though the actions may be captured for different PT records (ie, different onset for the PT with action “drug interrupted” and the PT with action “dose reduced”).

### **6.6.1.4. Adverse events leading to discontinuation of study treatment**

The frequency (number and percentage) of patients with each of the following will be presented for TEAEs leading to permanent discontinuation of each study drug and study treatment, by treatment group:

- TEAEs leading to discontinuation of avelumab by SOC and PT
- Related TEAEs leading to discontinuation of avelumab by SOC and PT

- TEAEs leading to discontinuation of axitinib by SOC and PT
- Related TEAEs leading to discontinuation of axitinib by SOC and PT
- TEAEs leading to discontinuation of any study drug by SOC and PT
- Related TEAEs leading to discontinuation of any study drug by SOC and PT
- TEAEs leading to discontinuation of all study drugs by SOC and PT
- Related TEAEs leading to discontinuation of all study drugs by SOC and PT

The listing of all AEs leading to treatment discontinuation will also be provided with the relevant information.

### **6.6.2. Deaths**

The frequency (number and percentage) of patients in the safety analysis set who died and who died within 30 days after last dose of study treatment as well as the reason for death, will be tabulated based on information from the ‘Notice of Death’ and ‘Survival Follow-Up’ eCRFs, by treatment group.

- All deaths
- Deaths within 30 days after last dose of study treatment
- Reason for Death
  - Disease progression
  - Study treatment toxicity
  - AE not related to study treatment
  - Unknown
  - Other.

In addition, date and cause of death will be provided in individual patient data listing together with selected dosing information (study treatment received, date of first / last administration, dose) and will include the following information:

- AEs with fatal outcome (list preferred terms of AEs with outcome=Fatal, as well as AEs of Grade 5),
- Flag for death within 30 days of last dose of study treatment

### **6.6.3. Serious adverse events**

The frequency (number and percentage) of patients with each of the following will be presented for treatment-emergent SAEs by treatment group:

- SAEs by SOC and PT

- Related SAEs by SOC and PT

The listings of all SAEs will also be provided with the relevant information with a flag for SAEs with onset outside of the on-treatment period.

#### **6.6.4. Other significant adverse events**

The frequency (number and percentage) of patients with each of the following will be presented for irAEs, by treatment group:

- irAEs leading to death, by Cluster and PT
- irAEs, by Cluster and PT
- irAEs, Grade  $\geq 3$ , by Cluster and PT
- irAEs leading to discontinuation of avelumab, by Cluster and PT
- irAEs leading to discontinuation of axitinib, by Cluster and PT
- irAEs leading to discontinuation of any study drug, by Cluster and PT
- irAEs leading to discontinuation of all study drugs, by Cluster and PT
- Serious irAEs, by Cluster and PT

The listing of all irAEs will also be provided with the relevant information with a flag for irAEs with onset outside of the on-treatment period.

The frequency (number and percentage) of patients with each of the following will be presented for IRRs, by treatment group:

- IRRs leading to death, by PT
- IRRs, by PT
- IRRs, Grade  $\geq 3$ , by PT
- IRRs leading to discontinuation of avelumab, by PT
- Serious IRRs, by PT
- Time related to first onset of an IRR (infusion 1, infusion 2, infusion 3, infusion 4 or later)

The listing of all IRRs will also be provided with the relevant information with a flag for IRRs with onset outside of the on-treatment period.

#### **6.6.5. Laboratory data**

##### **6.6.5.1. Hematology and chemistry parameters**

Laboratory results will be classified according to the NCI-CTCAE criteria version 4.03. Non-numerical qualifiers (with the exception of fasting flags) will not be taken into

consideration in the derivation of CTCAE criteria (eg, hypokalemia Grade 1 and Grade 2 are only distinguished by a non-numerical qualifier and therefore Grade 2 will not be derived). Additional laboratory results that are not part of NCI-CTCAE will be presented according to the categories: below normal limit, within normal limits and above normal limit (according to the laboratory normal ranges).

Quantitative data will be summarized using simple descriptive statistics (mean, SD, median, Q1, Q3, minimum, and maximum) of actual values and changes from baseline for each nominal visit over time (unscheduled measurements would therefore not be included in these summaries as described in Section 5.2.9). End of Treatment visit laboratory results will be summarized separately. The changes computed will be the differences from baseline. Qualitative data based on reference ranges will be described according to the categories (ie, Low, Normal, High).

Abnormalities classified according to NCI-CTCAE toxicity grading version 4.03 will be described using the worst grade. For those parameters which are graded with two toxicities such as potassium (hypokalemia/hyperkalemia), the toxicities will be summarized separately. Low direction toxicity (eg, hypokalemia) grades at baseline and post baseline will be set to 0 when the variables are derived for summarizing high direction toxicity (eg, hyperkalemia), and vice versa.

For **WBC differential counts** (total neutrophil [including bands], lymphocyte, monocyte, eosinophil, and basophil counts), the absolute value will be used when reported. When only percentages are available (this is mainly important for neutrophils and lymphocytes, because the CTCAE grading is based on the absolute counts), the absolute value is derived as follows:

$$\text{Derived differential absolute count} = (\text{WBC count}) \times (\text{Differential \%value} / 100)$$

If the range for the differential absolute count is not available (only range for value in % is available) then Grade 1 will be attributed to as follows:

- Lymphocyte count decreased:
  - derived absolute count does not meet Grade 2-4 criteria, and
  - % value < % LLN value, and
  - derived absolute count  $\geq 800/\text{mm}^3$
- Neutrophil count decreased
  - derived absolute count does not meet Grade 2-4 criteria, and
  - % value < % LLN value, and
  - derived absolute count  $\geq 1500/\text{mm}^3$

For **calcium**, CTCAE grading is based on Corrected Calcium and Ionized Calcium (CALCIO). Corrected Calcium is calculated from Albumin and Calcium as follows

Corrected Calcium (mmol/L) = measured total Calcium (mmol/L) + 0.02 (40 – serum Albumin [g/L]).

**Liver function tests:** Alanine aminotransferase (ALT), aspartate aminotransferase (AST), and total bilirubin (TBILI) are used to assess possible drug induced liver toxicity. The ratios of test result over upper limit of normal (ULN) will be calculated and classified for these three parameters during the on-treatment period.

Summary of liver function tests will include the following categories. The number and percentage of patients with each of the following during the on-treatment period will be summarized by treatment group:

- ALT  $\geq 3 \times \text{ULN}$ , ALT  $\geq 5 \times \text{ULN}$ , ALT  $\geq 10 \times \text{ULN}$ , ALT  $\geq 20 \times \text{ULN}$
- AST  $\geq 3 \times \text{ULN}$ , AST  $\geq 5 \times \text{ULN}$ , AST  $\geq 10 \times \text{ULN}$ , AST  $\geq 20 \times \text{ULN}$
- (ALT or AST)  $\geq 3 \times \text{ULN}$ , (ALT or AST)  $\geq 5 \times \text{ULN}$ , (ALT or AST)  $\geq 10 \times \text{ULN}$ , (ALT or AST)  $\geq 20 \times \text{ULN}$
- TBILI  $\geq 2 \times \text{ULN}$
- Concurrent ALT  $\geq 3 \times \text{ULN}$  and TBILI  $\geq 2 \times \text{ULN}$
- Concurrent AST  $\geq 3 \times \text{ULN}$  and TBILI  $\geq 2 \times \text{ULN}$
- Concurrent (ALT or AST)  $\geq 3 \times \text{ULN}$  and TBILI  $\geq 2 \times \text{ULN}$
- Concurrent (ALT or AST)  $\geq 3 \times \text{ULN}$  and TBILI  $\geq 2 \times \text{ULN}$  and ALP  $> 2 \times \text{ULN}$
- Concurrent (ALT or AST)  $\geq 3 \times \text{ULN}$  and TBILI  $\geq 2 \times \text{ULN}$  and (ALP  $\leq 2 \times \text{ULN}$  or missing)

Concurrent measurements are those occurring on the same date.

Categories will be cumulative, ie, a patient with an elevation of AST  $\geq 10 \times \text{ULN}$  will also appear in the categories  $\geq 5 \times \text{ULN}$  and  $\geq 3 \times \text{ULN}$ . Liver function elevation and possible Hy's Law cases will be summarized using frequency counts and percentages.

An evaluation of Drug-Induced Serious Hepatotoxicity (eDISH) plot will also be created, with different symbols for different treatment groups, by graphically displaying

- peak serum ALT(/ULN) vs peak total bilirubin (/ULN) including reference lines at ALT=3×ULN and total bilirubin=2×ULN.
- peak serum AST(/ULN) vs peak total bilirubin (/ULN) including reference lines at AST=3×ULN and total bilirubin=2×ULN.

In addition, a listing of all TBILI, ALT, AST and ALP values for patients with a post-baseline TBILI  $\geq 2 \times \text{ULN}$ , ALT  $\geq 3 \times \text{ULN}$  or AST  $\geq 3 \times \text{ULN}$  will be provided.

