7.1.3. Laboratory Safety Assessments

Haematology, blood chemistry, and urinalysis will be collected at the time points described in the [Schedule of Activities](#) table and analyzed at local laboratories. They may also be performed when clinically indicated. The required laboratory tests are listed in [Table 8](#). Clinically significant abnormal laboratory results should be repeated as soon as possible (preferably within 24-48 hours) and followed up as per standard clinical practice unless otherwise specified in this protocol.

If a full and core chemistry panel are scheduled at the same visit, then only the full chemistry panel will be performed.

Table 8. Required Laboratory Tests

Hematology	Chemistry Panel (* denotes core chemistry test)	After amendment #4 approval Chemistry Panel (# denotes test to be performed only when clinically indicated)	Urinalysis	Coagulation Tests	Pregnancy Tests
Hemoglobin	ALT*	ALT	Protein, glucose, blood. Urine dipstick/other semiquantitative method, for urine protein: if $\geq 2+$, collect 24-hour	PT, INR PTT or aPTT	For female patients of childbearing potential, serum or urine
Platelets	AST*	AST			
WBC	Alkaline Phosphatase*	Alkaline Phosphatase			
Absolute Neutrophils	Sodium*	Sodium			
Absolute Lymphocytes	Potassium*	Potassium			
Absolute Monocytes	Magnesium*	Magnesium			
Absolute Eosinophils	Chloride*	Chloride			
Absolute Basophils	Total Calcium*	Total Calcium			
	Total Bilirubin* °	Total Bilirubin °			
	BUN or Urea*	BUN or Urea			
	Creatinine*	Creatinine			
	Glucose (non-fasted)*	Glucose (non-fasted)			
	Phosphorus or Phosphate*	Phosphorus or Phosphate			
	Albumin	Albumin [#]			
	Total Protein	Total Protein [#]			
	Uric Acid	Uric Acid [#]			
	Amylase	Amylase			
	Gamma glutamyl transferase (GGT)	Gamma glutamyl transferase (GGT)			
	Cholesterol	Cholesterol [#]			
	Creatine kinase	Creatine kinase			
	C-reactive protein (CRP)	C-reactive protein (CRP) [#]			
	Lactate dehydrogenase (LDH)	-			
	Lipase	Lipase			
	Triglycerides	Triglycerides [#]			
	Other tests: HBV, HCV				
	Thyroid Function Tests: TSH, free T4				

090177e1907c3de0\0.1\Draft\Versioned On:01-Mar-2019 17:22 (GMT)

	Other Tests: ACTH			
--	-----------------------------	--	--	--

° For potential Hy's Law cases, in addition to repeating AST and ALT, laboratory tests should include albumin, creatine kinase, total bilirubin, direct and indirect bilirubin, gamma glutamyl transferase, prothrombin time (PT)/INR, alkaline phosphatase.

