### **Parameters with NCI-CTC grades not available:**

Hematology and chemistry evaluations which cannot be graded per CTCAE criteria will be summarized as frequency (number and percentage) of patients with:

- shifts from baseline normal to at least one result above normal during on-treatment period
- shifts from baseline normal to at least one result below normal during on-treatment period

In this study, these apply to the following parameters:

- Hematology: Absolute Monocytes, Absolute Eosinophils, Absolute Basophils

- Serum Chemistry: Chloride, Total Urea, Uric Acid, Total Protein, C-Reactive Protein, Lactate Dehydrogenase (LDH), TSH, Free T4, ACTH, ANA (performed at baseline and if clinically indicated), ANCA (performed at baseline and if clinically indicated), RF (performed at baseline and if clinically indicated), HBV and HCV (performed at baseline and if clinically indicated).

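### Six chemistry tests become indication-only after Amendment 4, but SAP 6.6.5.1 still summarises them at every nominal visit, so late-visit means may come partly or wholly from selected patients

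*SAP*

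**What the plan says.** **Sampling.** Before Amendment 4, the chemistry footnotes to both treatment-period Schedules of Activities require the full panel at screening, on Day 1 of Cycles 1, 2, 4 and 7, and every 6 weeks thereafter. After approval of the amendment, chemistry is required every 6 weeks. Table 8 (Protocol 7.1.3) has a separate column for the post-amendment panel, with a hash sign that "denotes test to be performed only when clinically indicated". Six tests carry it: albumin, total protein, uric acid, cholesterol, C-reactive protein and triglycerides. LDH has a dash in that column.

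**Analysis.** SAP 6.6.5.1 summarises quantitative laboratory data by mean, SD, median, quartiles and range "of actual values and changes from baseline for each nominal visit over time". It adds that unscheduled measurements are left out, as SAP 5.2.9 describes; that section limits by-visit statistics to data from scheduled visits. SAP 5.3.1 analyses data as observed, without imputation. For tests without CTCAE grades, SAP 6.6.5.1 also counts patients with "shifts from baseline normal to at least one result above normal during on-treatment period", and the corresponding shifts below normal. The readable SAP text does not mention Amendment 4 or make an exception for the six tests.

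**The concern.** A by-visit mean describes time on drug only if roughly the same kind of patient is measured at each visit. For these six tests the rule changes from everyone to patients with a clinical reason. A patient tested because a problem is suspected is more likely to have an abnormal value, so the mean can move although nothing has changed in the treated population.

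The study has no feature that would expose such an artefact. SAP 6 states that only DL1 and DL1 with lead-in are reported and that there is no randomisation, so there is no concurrent comparator under the same sampling rule. About 55 patients are projected (SAP 2.2), so few may contribute to late visits. A drift in C-reactive protein, albumin or lipids could be read as a late effect of the combination.

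**Working it through.** The plan states no figure on this point, so there is none to reproduce. The check compares the rules and then asks whether a size can be given.

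**1. Follow one result through the rules.** A patient attends a 6-weekly visit after the amendment, and the investigator adds an albumin because of a suspected problem.

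| Step | Source | Result |
|---|---|---|
| Is albumin routine? | Protocol Table 8, post-amendment column | No, only if indicated |
| Is the visit scheduled? | Schedule of Activities, chemistry footnotes | Yes, every 6 weeks |
| Is the result excluded from by-visit statistics? | SAP 5.2.9 | No, the filter is on visit type |
| Is anything entered for untested patients? | SAP 5.3.1 | No, as observed |
| Is there an exception for this test? | SAP 6.6.5.1 | None |

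The albumin enters the visit mean. The same albumin drawn at an unscheduled visit would not.

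**2. Does the SAP recognise indication-only tests elsewhere?** Yes. In the list of parameters without CTCAE grades, ANA, ANCA, RF, HBV and HCV are annotated as done at baseline and if clinically indicated. Uric acid, total protein and C-reactive protein stand in the same list without that note.

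**3. Who is affected, and when?** The switch follows the calendar date of approval, not the visit number. Patients who passed a given visit before that date were tested routinely; those who reach it later are tested selectively. One visit can hold both. SAP 2 sets the primary cut-off 18 months after the last patient's first dose and the final analysis after last patient last visit. The approval date relative to that cut-off is not given, so only the final analysis clearly reaches the post-amendment period.

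**4. Can a size be given?** Only under assumptions, none of them from the documents. Let f be the share of post-amendment patients tested, r the correlation between suspicion and the test value, and q the share of patients who passed the visit before the amendment. Assume a true mean change of zero and suspicion in one direction only.

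- Shift among selected patients, in SD: b = r × φ(z₁₋f) / f.
- Weight of selected patients in the visit mean: w = (1 − q)f / [(1 − q)f + q].
- Shift of the visit mean: b × w.

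Example with f = 0.2 and r = 0.5: b = 0.5 × 0.280 / 0.2 = 0.70 SD. With q = 0.5, w = 0.1 / 0.6 = 0.167, and the shift is 0.12 SD. With q = 0.9, w = 0.02 / 0.92 = 0.022, and the shift is 0.02 SD.

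| q | Shift over f = 0.1 to 0.3 and r = 0.3 to 0.8 |
|---|---|
| 0 | 0.35 to 1.40 SD |
| 0.5 | 0.05 to 0.21 SD |
| 0.9 | 0.01 to 0.03 SD |

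The result runs from negligible to large, depending mainly on q, which is unknown. The table shows only that the size is undetermined.

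**The case against.** **Unscheduled measurements are already excluded.** After the amendment these tests are not scheduled at any visit, so the exclusion in SAP 6.6.5.1 could be read to cover them. No passage says how the eCRF labels such draws. This has force: the text is ambiguous. However, SAP 6.6.5.1 refers to SAP 5.2.9 for the rule, and that section defines it by visit. Under that wording the draw stays in, so the ambiguity is itself a reason to add a sentence.

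**The fall in numbers would be visible.** SAP 5.2.3 requires the counts of non-missing and missing values for continuous variables. This stands and lessens the risk of misreading. It shows that testing became sparse, but not that the tested patients were chosen for a reason.

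**The stakes are low.** There is no formal hypothesis testing (SAP 5.1.1), DLTs concern the first 4 weeks, and worst-grade tables, shift tables and listings capture abnormal results. All of this stands.

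**LDH.** A reader might infer that LDH has the same defect. The documents do not support that. LDH leaves the panel, so its late visits have few or no values and selection by indication is not the issue. Cutting its on-treatment shift count at the amendment date would remove only ad hoc results, which may carry a safety signal, while later results for the six other tests stay in such tables.

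**Conclusion.** The point holds as a gap in the SAP. Its rules, as written, let indication-driven results for six tests into nominal-visit statistics, so late-visit summaries may come partly or wholly from patients selected for a suspected abnormality. This rests on two readings: that SAP 5.2.9 works by visit type, and that some indicated draws are made at scheduled visits.

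Three stronger conclusions are tempting and unsupported. First, that post-amendment visit means describe only suspected cases: a visit can mix routinely and selectively tested patients. Second, that the bias is 0.35 to 1.40 SD: that range needs every patient to reach the visit after the amendment, and its other inputs are assumed. Third, that the primary analysis is distorted: the documents do not place the amendment before or after its cut-off.

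The size is unknown. The consequence is limited to descriptive by-visit safety summaries of six tests, mainly at the final analysis.

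**What to change.** Add one sentence to SAP 6.6.5.1: results for albumin, total protein, uric acid, cholesterol, C-reactive protein and triglycerides obtained after Amendment 4 took effect at the patient's site are handled as unscheduled. They are left out of the nominal-visit descriptive statistics and kept in listings and in worst-grade or shift tables. No change is needed for LDH.

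The cost is the wording and one effective date per site, which the documents do not show to be in the analysis data already. Late-visit summaries for these six tests become shorter. No new data collection is needed, and no abnormal result is lost from the safety tables.
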